10.2.2 Adverse Event Overview

An overview of AEs will be presented consisting of the number and percentage of participants experiencing at least one event for each of the following AE categories:

- Any treatment-emergent AE
- Any treatment-emergent AE related to study treatment according to the investigator
- Any treatment-emergent AE Grade 3 or higher
- Any serious treatment-emergent AE
- Any treatment-emergent AE leading to discontinuation of study treatment
- Any treatment-emergent AE leading to interruption of study treatment
- Any treatment-emergent AE leading to death
- All deaths

10.2.3 Treatment-Emergent Adverse Events by SOC and/or PT

Treatment-emergent adverse events will be summarized by SOC and PT; by maximum relationship to study treatment as assessed by the investigator (e.g., reasonable possibility or no reasonable possibility) and SOC and PT; by maximum grade and SOC and PT; and

by Participant number and SOC and PT. Specific adverse events will be counted once for each Participant for calculating percentages, unless stated otherwise. In addition, if the same adverse event occurs multiple times within a Participant, the highest severity and level of relationship to investigational product will be reported.

In addition, treatment-emergent adverse events will be summarized by PT and sorted by decreasing frequency for the total active group.

10.2.4 Deaths, Serious Adverse Events, and Adverse Events Leading to Study Treatment Discontinuation

Treatment-emergent serious adverse events (SAEs), TEAEs leading to premature discontinuation of study treatment, and TEAEs leading to death will be summarized by SOC and PT.

Tabular listings will be provided for all deaths, TESAEs, and TEAEs leading to premature discontinuation of study treatment.

10.3 Analysis of Laboratory Data

The clinical laboratory tests defined in the protocol operations manual (e.g., hematology, clinical chemistry, and urinalysis) will be summarized.

Each laboratory variable will be summarized for all time points (starting with Baseline) with the number of non-missing observations, mean and standard deviation, median, minimum and maximum. Mean change from baseline to each applicable post-baseline visit will be summarized for select laboratory variables, with the number of observations, baseline mean, and visit mean. The change from baseline mean, standard error, and 95% confidence interval will be presented for the mean change from baseline within each treatment group. The select laboratory variables include alanine aminotransferase (ALT), aspartate aminotransferase (AST), bilirubin, alkaline phosphatase, hemoglobin, hematocrit, neutrophils, lymphocytes, monocytes, eosinophils, absolute platelet count, blood urea nitrogen (BUN), creatinine and glomerular filtration rate (GFR).

Changes in laboratory parameters will be tabulated using shift tables the by National Cancer Institute (NCI) Common Terminology Criteria (CTC) version 4.03. Shift tables from baseline to worst post-baseline value and baseline to final treatment period value will be presented by treatment group.

[figure not shown]
Laboratory abnormalities meeting NCI-CTC grade 3 and 4 will be summarized.

Laboratory values will also be categorized as low, normal, or high based on the normal ranges of the laboratory used for each sample. Shift tables from low or normal baseline to high post-baseline, and from normal or high baseline to low post-baseline will be presented by treatment group. This will be repeated for the shift to final treatment period value based on the lab normal ranges.

Laboratory abnormalities will be evaluated based on Potentially Clinically Significant (PCS) criteria (Appendix B). For each laboratory PCS criterion, the number and percentage of participants who have a laboratory value meeting the criteria will be summarized. Listings will be provided to summarize Participant-level laboratory data for participants meeting PCS criteria.

The following criteria will be used to assess for potential hepatotoxicity. The number and percentage of participants meeting each of the following criteria will be summarized by treatment group, and a listing of ALT, AST, bilirubin, and alkaline phosphatase at each time for all participants that met any of the criteria below at any time will be produced.

- ALT > $3 \times ULN$, > $5 \times ULN$, > $10 \times ULN$, > $20 \times ULN$
- AST > $3 \times ULN$, > $5 \times ULN$, > $10 \times ULN$, > $20 \times ULN$
- TBL > $1.5 \times ULN$, > $2 \times ULN$
- ALT and/or AST $> 3 \times ULN$ and bilirubin $> 1.5 \times ULN$
- ALT and/or AST $> 3 \times ULN$ and bilirubin $> 2 \times ULN$
- ALT $> 3 \times ULN$ and bilirubin $> 1.5 \times ULN$
- ALT $> 3 \times ULN$ and bilirubin $> 2 \times ULN$
- Alkaline phosphatase $> 1.5 \times ULN$

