7.5 Statistical Analyses for Safety

General Considerations

Safety analyses will be carried out using the safety analysis set. Safety will be assessed by AEs, lab values, vital sign measurements, ECG, and C-SSRS. For continuous safety outcomes, the change from Baseline will be analyzed in a descriptive manner by treatment group and by visit. For categorical safety outcomes, the number and percentage of participants in each category will be summarized by treatment group and by visit. Shift of laboratory values from Baseline to defined time points will be tabulated. Hypothesis testing will not be performed for safety parameters.

Analysis of Adverse Events

All AEs will be coded using the current version of the Medical Dictionary for Regulatory Activities (MedDRA). The number and percentage of participants with TEAEs, treatment-emergent SAEs, AEs with a reasonable possibility of being related to study drug, and AEs leading to study drug discontinuation will be summarized by treatment group and will be tabulated using primary MedDRA system organ class (SOC) and preferred term (PT). Treatment-emergent AEs will be defined as all events that begin or worsen (increased in intensity or became serious) on or after first dose of study drug. An AE occurs more than 30 days after the last dose will not be counted as a TEAE.

Analysis of Laboratory Data

Changes from Baseline in continuous laboratory parameters will be summarized by n, mean, standard deviation, minimum value, median, and maximum value for each treatment group and all participants overall for each continuous hematology, chemistry, and urinalysis variable.

Laboratory observations will be categorized according to CTCAE Version 4.0 and higher. For each hematology, chemistry, and urinalysis with a reference range, shift tables will be prepared for shifts from baseline to highest post-baseline grade and shifts from Baseline to the final value during the entire study for each treatment group.

Analysis of Vital Signs

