12.0 Interim Analyses

One unblinded interim analysis is planned for this study, which will take place when 50% of participants (approximately 30/treatment group) have completed the Week 6 visit (including those who discontinue prior to the Week 6 visit) and the database has been locked for the interim analysis.

The interim analysis will include the following endpoints and analyses:

- Demographics and baseline characteristics
- Primary Endpoint:
 - Change from baseline to Week 6 in ADAS-Cog 14 total score

• Other Endpoints:

- Change from baseline to Week 6 in ADAS-Cog 14 total score
- Change from baseline to Week 6 in Cogstate Computerized Battery (CCB)
 Composite and Individual Scores
- Summary of Safety:
 - AE overview, TEAE by SOC and PT, SAE by SOC and PT
 - Summary of potentially clinically significant laboratory tests and vital sign values

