Appendix B. Potentially Clinically Significant Criteria for Safety Endpoints

The criteria for Potentially Clinically Significant (PCS) laboratory findings are described in Table B-1, Table B-2, and Table B-3, PCS criteria for vital sign and weight findings are described in Table B-4, and PCS criteria for ECG are described in Table B-5.

Table B-1. Criteria for Potentially Clinically Significant Hematology Values

Hematology	PCS Low	PCS High
White blood cells	$< 3.0 \times 10^{9}/L$	$> 16.0 \times 10^9/L$
Lymphocytes	$< 0.8 \times 10^9/L$	$> 12.0 \times 10^9/L$
Neutrophils	$< 1.5 \times 10^9 / L$	$> 13.5 \times 10^9/L$
Monocytes	N/A	$> 2.5 \times 10^9 / L$
Eosinophils	N/A	$> 1.6 \times 10^9/L$
Basophils	N/A	$> 1.6 \times 10^9/L$
Red blood cells	$\leq 3.5 imes 10^{12}/L$	$\geq 6.4 \times 10^{12}/L$
Hemoglobin – Females	≤ 95 g/L	≥ 175 g/L
Hemoglobin – Males	≤ 115 g/L	≥ 190 g/L
Hematocrit – Females	≤ 32%	≥ 54%
Hematocrit – Males	≤ 37%	≥ 60%
Platelets	$\leq 75 \times 10^9 / L$	$\geq 700 \times 10^9 / L$

N/A = Not applicable; PCS = potentially clinically significant; ULN = upper limit of normal

Note: A post-baseline value must be more extreme than the baseline value to be considered a Potentially Clinically Significant finding.

Values from CTCAE v4.03.

Table B-2. Criteria for Potentially Clinically Significant Chemistry Values

Blood Chemistry	PCS Low	PCS High
Alanine aminotransferase (ALT)	N/A	3 × ULN
Aspartate aminotransferase (AST)	N/A	$3 \times ULN$
Alkaline phosphatase (ALP)	N/A	$3 \times ULN$
Total bilirubin	N/A	$> 1.5 \times ULN$
Blood urea nitrogen (BUN)	N/A	$\geq 10.7 \text{ mmol/L}$
Creatinine	N/A	$\geq 176.8 \text{ umol/L}$
Sodium	$\leq 126 \text{ mmol/L}$	$\geq 156 \text{ mmol/L}$
Potassium	\leq 3 mmol/L	\geq 6 mmol/L
Chloride	\leq 90 mmol/L	$\geq 118 \text{ mmol/L}$
Bicarbonate	$\leq 16 \text{ mmol/L}$	\geq 35 mmol/L
Glucose	\leq 2.2 mmol/L	\geq 9.7 mmol/L
Calcium	\leq 2 mmol/L	\geq 3 mmol/L
Phosphorus	$\leq 0.6 \text{ mmol/L}$	$\geq 1.7 \text{ mmol/L}$
Albumin	\leq 25 g/L	$\geq 625 \text{ g/L}$
Total protein	≤ 45 g/L	$\geq 100 \text{ g/L}$

N/A = Not applicable; PCS = potentially clinically significant; ULN = upper limit of normal

Note: A post-baseline value must be more extreme than the baseline value to be considered a Potentially Clinically Significant finding.

Values from CTCAE v4.03.

Table B-3. Criteria for Potentially Clinically Significant Urinalysis Values

Urinalysis	PCS Low	PCS High
Glucose	N/A	≥ ++++ (+4)
Ketones	N/A	≥ ++++ (+4)

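### SAP Table B-2: no valid result can reach the albumin PCS High limit of 625 g/L, so the high-albumin count is zero by construction

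*SAP*

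**What the plan says.** SAP 10.3 (Analysis of Laboratory Data) makes Appendix B operative: "Laboratory abnormalities will be evaluated based on Potentially Clinically Significant (PCS) criteria (Appendix B". It then fixes the output: "For each laboratory PCS criterion, the number and percentage of participants who have a laboratory value meeting the criteria will be summarized". Participant-level listings go with the counts.

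The limits are in SAP Appendix B, Table B-2. Two adjacent rows matter, both in g/L:

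| Analyte | PCS Low | PCS High |
|---|---|---|
| Albumin | 25 or below | 625 or above |
| Total protein | 45 or below | 100 or above |

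A note under the table adds a condition: "A post-baseline value must be more extreme than the baseline value to be considered a Potentially Clinically Significant finding". A further note attributes the table's values to CTCAE v4.03.

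The PCS summary is used twice. Besides the final tables, SAP 12.0 (Interim Analyses) includes "Summary of potentially clinically significant laboratory tests and vital sign values". Neither the protocol nor the SAP gives another PCS limit for albumin or explains the figure of 625.

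**The concern.** A PCS threshold is useful only if some participant could cross it. Albumin is one component of total protein, so a participant's albumin cannot exceed their total protein. The table treats total protein of 100 g/L as abnormally high, yet raises no high-albumin flag until albumin alone reaches 625 g/L.

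If the table is programmed as printed, the high-albumin criterion is inert. A zero for every arm would then come from the limit and not from the participants, but someone reading the PCS table alone could take it as an observed absence of high values. The same limit would carry into the interim PCS laboratory summary. If the criterion ever did fire, it would point to a unit or transcription error in the data and not to a clinical finding.

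**Working it through.** The limit is a stated constant, not derived from other inputs, so there is no plan calculation to reproduce. The check compares it with its neighbours in SAP Table B-2.

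**1. Against total protein (same table, same unit).**
- Albumin PCS High: 625 g/L. Total protein PCS High: 100 g/L.
- Ratio: 625 / 100 = 6.25.
- Total protein = albumin + other proteins, and the second term cannot be negative. Albumin of 625 g/L or more therefore requires total protein of 625 g/L or more, at least 6.25 times the level the table already calls PCS High.

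**2. Against albumin's own low limit.**
- 625 / 25 = 25.

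**3. Against the high/low ratio of every other chemistry row with two limits.**

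| Row | High / Low | Ratio |
|---|---|---|
| Sodium | 156 / 126 | 1.24 |
| Chloride | 118 / 90 | 1.31 |
| Calcium | 3 / 2 | 1.50 |
| Potassium | 6 / 3 | 2.00 |
| Bicarbonate | 35 / 16 | 2.19 |
| Total protein | 100 / 45 | 2.22 |
| Phosphorus | 1.7 / 0.6 | 2.83 |
| Glucose | 9.7 / 2.2 | 4.41 |
| **Albumin** | **625 / 25** | **25.00** |

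The other eight rows run from 1.24 to 4.41, and albumin is the only one outside that range. This step does not prove an error, because analytes differ in their natural spread, but it agrees with step 1.

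**4. Effect on the output.** No valid result meets the criterion, so the high-albumin count is 0 in each arm, in the final tables and at the interim. The more-extreme-than-baseline condition can only remove flags, so it does not help.

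**5. What still works.** The albumin-low criterion is separate and unaffected. SAP 10.3 also summarizes each laboratory variable at every time point, including the maximum. It gives shift tables to high values based on the laboratory's normal ranges, repeated for the final treatment-period value. High albumin can show in both.

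How many participants a correct limit would flag cannot be computed, because the documents do not give that limit.

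**The case against.** The strongest objection is that 625 may not be the sponsor's number at all. Tables can be damaged in conversion from PDF to text, and Appendix B shows signs of this: the multiplication sign in the red blood cell row of Table B-1 is garbled. In Table B-2 the ALT, AST and ALP limits carry no comparison sign, although that could be in the source. One misread cell cannot be excluded. Against this, decimals survive elsewhere in the same table (10.7, 176.8, 2.2, 9.7, 0.6, 1.7), and the albumin entry itself is unambiguous. What stands is that the original page must be checked first.

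The second objection is that little is lost, and this also stands. The output is descriptive; Protocol 7.5 says "Hypothesis testing will not be performed for safety parameters". Albumin is not among the variables that SAP 10.3 selects for mean change from baseline, nor in its hepatotoxicity criteria. SAP 12.0 attaches no decision rule to albumin.

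A reader might infer three stronger things that the documents do not support:
- **That albumin drops out of the PCS summary.** Only the high side is inert.
- **That high albumin would go unseen.** The by-visit maximum and the shift tables remain.
- **That a decimal point was dropped and 62.5 g/L was meant.** Nothing in either document supports that value over any other.

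**Conclusion.** The albumin PCS High entry in SAP Table B-2 is wrong as written. It is 6.25 times the table's own high limit for total protein, and no valid result can meet it. One planned count and its listing, and the corresponding interim entry, are zero by construction.

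This rests on two assumptions. The first is that albumin is a component of total protein and that no valid result approaches 625 g/L; this is general knowledge, not stated in the documents. The second is that the printed entry really reads 625 g/L.

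The consequence is minor. No efficacy or safety conclusion is shown to change, and the number of participants a correct limit would flag is unknown and probably small. The case for correcting it is that a criterion the SAP undertakes to report should be able to return something other than zero.

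**What to change.** Check the albumin PCS High entry in Table B-2 against the original SAP page, against the source that the table note names, and against the unit in which the laboratory reports albumin. Then correct it in Table B-2 and in the PCS program before the tables are run. If an interim summary was already produced with this limit, rerun or footnote its high-albumin entry. The intended value is for the sponsor to supply.

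The cost is one cell in the appendix and one constant in the program. No data collection, sample size or other analysis is affected.

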10.4 Analysis of Vital Signs and Weight

Vital sign measurements of systolic and diastolic blood pressure, pulse rate, and body temperature will be summarized.

Each vital sign variable and weight will be summarized for all time points (starting with Baseline) with the number of non-missing observations, mean and standard deviation, median, minimum and maximum. Mean change from baseline to each applicable post-baseline visit will be summarized for each vital sign variable, with the number of observations, baseline mean, and visit mean. The change from baseline mean, standard error, and 95% confidence interval will be presented within each treatment group.

[figure not shown]
Vital sign variables and weight will be evaluated based on Potentially Clinically Significant (PCS) criteria (Appendix B). For each vital sign PCS criterion, the number and percentage of participants who have a vital sign value meeting the criteria will be summarized. Listings will be provided to summarize Participant-level vital sign and weight data for participants meeting PCS criteria.

10.5 Other Safety Analyses

10.5.1 ECG

The number and percentage of participants with Normal and electrocardiogram (ECG) readings will be summarized at each visit ECG is performed. The number and percentage of participants with baseline Normal or Abnormal ECG and shifted to post-baseline (worst) Abnormal or Normal will be summarized in a shift table.

Descriptive statistics for ECG parameters (heart rate, RR interval, PR interval, QRS duration, QT interval, and QT interval corrected for heart rate [QTc]) at baseline, postbaseline, and changes from baseline values at each assessment time point to the end of study will be presented by treatment group. The QTc will be calculated using both the Bazett and Fridericia corrections (QTcB and QTCF).

The number and percentage of participants with PCS ECG values according to Table B-5 at any time post-baseline will be summarized. Listings will be provided to summarize Participant-level ECG data for participants meeting PCS criteria.

10.5.2 C-SSRS

For C-SSRS, given sufficient data, the number and percentage of participants with suicidal ideation and/or suicidal behavior as recorded on the C-SSRS will be summarized by treatment group. The summary of responses for most severe suicidal ideation and most sever suicidal behavior in the participant's lifetime history, in the past 2 years, in the past 12 months, during the double-blinded treatment period, and during the follow-up period will be presented by each treatment group, active total and overall. A listing will also be prepared that includes all participants with 1 or more affirmative responses.

10.6 Safety Subgroup Analyses

The AE Overview and TEAE by SOC and PT summaries will be provided for the subset of participants taking symptomatic medication for AD at baseline and those who are not.

11.0 Other Analyses

All planned analyses are listed in the previous sections.

12.0 Interim Analyses

One unblinded interim analysis is planned for this study, which will take place when 50% of participants (approximately 30/treatment group) have completed the Week 6 visit (including those who discontinue prior to the Week 6 visit) and the database has been locked for the interim analysis.

The interim analysis will include the following endpoints and analyses:

- Demographics and baseline characteristics
- Primary Endpoint:
 - Change from baseline to Week 6 in ADAS-Cog 14 total score

• Other Endpoints:

- Change from baseline to Week 6 in ADAS-Cog 14 total score
- Change from baseline to Week 6 in Cogstate Computerized Battery (CCB)
 Composite and Individual Scores
- Summary of Safety:
 - AE overview, TEAE by SOC and PT, SAE by SOC and PT
 - Summary of potentially clinically significant laboratory tests and vital sign values

13.0 Overall Type-I Error Control

This is a Phase 2b dose-ranging and hypothesis generating study; therefore, there will be no control of Type I error for testing multiple doses, multiple endpoints, or interim analyses in this study.

14.0 Version History

Table 3. SAP Version History Summary

[figure not shown]
Version	Date	Summary	
1.0	12 July 2023	Initial version	
2.0	2 May 2024	Update to clarify the definition of analysis sets.	
		Update to clarify the definition of number of capsules that should have been taken.	
		Update to exclude efficacy data collected after blind broken.	
		Update to replace posterior probability with p-value statistic to efficacy analysis.	
		Added sensitivity analysis to primary endpoint using safety analysis set.	
		Removed weight-by-sex summary analysis.	
		Update to modify C-SSRS analysis.	
		Removed lab/vital sign comparison between treatment groups	
3.0	20 September 2024	Updated analysis for vital signs.	
		Added language for conducting additional subgroup analysis given sufficient data.	

14.1 Changes to Planned Analyses in the Protocol

There are currently no changes to the planned analyses in the protocol.

Appendix B. Potentially Clinically Significant Criteria for Safety Endpoints

The criteria for Potentially Clinically Significant (PCS) laboratory findings are described in Table B-1, Table B-2, and Table B-3, PCS criteria for vital sign and weight findings are described in Table B-4, and PCS criteria for ECG are described in Table B-5.

Table B-1. Criteria for Potentially Clinically Significant Hematology Values

Hematology	PCS Low	PCS High
White blood cells	$< 3.0 \times 10^{9}/L$	$> 16.0 \times 10^9/L$
Lymphocytes	$< 0.8 \times 10^9/L$	$> 12.0 \times 10^9/L$
Neutrophils	$< 1.5 \times 10^9 / L$	$> 13.5 \times 10^9/L$
Monocytes	N/A	$> 2.5 \times 10^9 / L$
Eosinophils	N/A	$> 1.6 \times 10^9/L$
Basophils	N/A	$> 1.6 \times 10^9/L$
Red blood cells	$\leq 3.5 imes 10^{12}/L$	$\geq 6.4 \times 10^{12}/L$
Hemoglobin – Females	≤ 95 g/L	≥ 175 g/L
Hemoglobin – Males	≤ 115 g/L	≥ 190 g/L
Hematocrit – Females	≤ 32%	≥ 54%
Hematocrit – Males	≤ 37%	≥ 60%
Platelets	$\leq 75 \times 10^9 / L$	$\geq 700 \times 10^9 / L$

N/A = Not applicable; PCS = potentially clinically significant; ULN = upper limit of normal

Note: A post-baseline value must be more extreme than the baseline value to be considered a Potentially Clinically Significant finding.

Values from CTCAE v4.03.

Table B-2. Criteria for Potentially Clinically Significant Chemistry Values

Blood Chemistry	PCS Low	PCS High
Alanine aminotransferase (ALT)	N/A	3 × ULN
Aspartate aminotransferase (AST)	N/A	$3 \times ULN$
Alkaline phosphatase (ALP)	N/A	$3 \times ULN$
Total bilirubin	N/A	$> 1.5 \times ULN$
Blood urea nitrogen (BUN)	N/A	$\geq 10.7 \text{ mmol/L}$
Creatinine	N/A	$\geq 176.8 \text{ umol/L}$
Sodium	$\leq 126 \text{ mmol/L}$	$\geq 156 \text{ mmol/L}$
Potassium	\leq 3 mmol/L	\geq 6 mmol/L
Chloride	\leq 90 mmol/L	$\geq 118 \text{ mmol/L}$
Bicarbonate	$\leq 16 \text{ mmol/L}$	\geq 35 mmol/L
Glucose	\leq 2.2 mmol/L	\geq 9.7 mmol/L
Calcium	\leq 2 mmol/L	\geq 3 mmol/L
Phosphorus	$\leq 0.6 \text{ mmol/L}$	$\geq 1.7 \text{ mmol/L}$
Albumin	\leq 25 g/L	$\geq 625 \text{ g/L}$
Total protein	≤ 45 g/L	$\geq 100 \text{ g/L}$

N/A = Not applicable; PCS = potentially clinically significant; ULN = upper limit of normal

Note: A post-baseline value must be more extreme than the baseline value to be considered a Potentially Clinically Significant finding.

Values from CTCAE v4.03.

Table B-3. Criteria for Potentially Clinically Significant Urinalysis Values

Urinalysis	PCS Low	PCS High
Glucose	N/A	≥ ++++ (+4)
Ketones	N/A	≥ ++++ (+4)
Protein	N/A	≥ ++ (+2)

N/A = Not applicable; PCS = potentially clinically significant; ULN = upper limit of normal

Note: A post-baseline value must be more extreme than the baseline value to be considered a Potentially Clinically Significant finding.

Values from CTCAE v4.03.

Table B-4. Criteria for Potentially Clinically Significant Vital Sign Values

Vital Signs	Very Low (VL)	Very High (VH)
Systolic Blood Pressure (mmHg)	< 90 or decreased ≥ 30 from baseline	> 160 or increased ≥ 40 from baseline
Diastolic Blood Pressure (mmHg)	< 50 or decreased ≥ 20 from baseline	> 100 or increased ≥ 30 from baseline
Pulse (bpm)	< 60 or decreased ≥ 30 from baseline	> 100 or increased ≥ 30 from baseline
Temperature (°C)	< 36 or decreased ≥ 1.1 from baseline	> 38 or increased ≥ 1.1 from baseline
Weight (kg)	Decreased ≥ 7% from baseline	Increased > 7% from baseline

bpm = beats per minute

Note: A post-baseline value must be more extreme than the baseline value to be considered a Potentially Clinically Significant finding.

Table B-5. Criteria for Potentially Clinically Significant Electrocardiograms

Parameter	Criteria	
QRS duration	≥ 150 msec	
PR interval	\geq 250 msec	
QTcF interval	> 450 msec, > 480 msec, > 500 msec	
QTcF interval	Increase from baseline > 60 msec	
QTcF interval	Increase from baseline > 30 msec but ≤ 60 msec	
QTcB interval	> 500 msec	
QTcB interval	Increase from baseline > 60 msec	

Note: A post-baseline value must be more extreme than the baseline value to be considered a Potentially Clinically Significant finding.

ABBV-552
M23-515 – Statistical Analysis Plan
Version 3 – 20 September 2024

